8.1 Timing of Analyses

Based on interim analyses for futility, it was decided to halt recruitment beginning January 19, 2021. The final data analyses will begin:

- after all 30-day post drug follow-up has been completed for all randomized patients,
- after chart review and data cleaning according to the data management plan are complete, and
- after approval of this SAP document by the study team.

8.2 Analysis Populations

8.2.1 Modified Intent to Treat Population (mITT) and Safety Population

All randomized patients who received at least one dose of dipyridamole or placebo will be included in the mITT population. The safety population will be the same as the mITT population. The mITT population will serve as the basis for comparisons of dipyridamole versus placebo and for assessment of safety.

8.3 Covariates and Subgroups

Models to compare dipyridamole versus placebo will include both stratification factors as predictors: sex and age. The analysis will include interactions between study drug and stratification factors. Age will be modelled both as a continuous covariate and as a grouping factor (in separate models). For longitudinal responses, models will also include days since first drug administration. Where appropriate, models will include baseline values of the response variable.

The win ratio analysis for the clinical hierarchical composite endpoint will be stratified according to age and sex (Dong et al., 2018).

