6.1 General Study Design and Plan

[figure not shown]
Our primary hypotheses are that patients on dipyridamole will evidence a smaller increase in D-dimer levels and better clinical outcomes on the COVID ordinal score than patients on placebo.

This is a proof-of-concept, placebo-controlled, single-blinded, randomized, 14-day trial of 160 patients.

Participants were assigned treatments to dipyridamole or placebo in 1:1 fashion using stratified, random blocks based on sex and age (above/below 65). Stratified blocks were generated using the ‘blockrand’ package in R.

After randomization, treatment was administered four times daily up until hospital discharge or 14 days, with clinical evaluations made daily. Clinically significant abnormal lab studies were evaluated for relationship to the study drug. Clinical data capture and survival follow-up occurred on Day 28 \pm 1. Patient follow-up occurred again 30 days after last dose of study drug. The study schematic is presented in Figure 1.

Figure 1 Schematic Representation of Study Design

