6.4.10 Modified WHO COVID-19 8-point Ordinal scale assessment

Ordinal scale assessments will be made daily and on Day 28 as below:

Table 2. Modified COVID 8-Point Ordinal Scale

Patient State	Descriptor	COVID Ordinal Score
Dead	Death	8
Hospitalized – severe disease	Ventilation + additional organ support (pressors, renal replacement therapy, ECMO)	7
	Intubation and mechanical ventilation	6
	Non-invasive ventilation or high-flow oxygen	5
Hospitalized – mild disease	Oxygen by mask or nasal prongs	4
	Hospitalized, no oxygen therapy	3
Ambulatory	Limitation of activities	2
	No limitation of activities	1

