9.4 Demographic and Baseline Variables

Demographic variables for participants will be:

1. Age in years at consent
2. Dichotomized age (≤ 65 or > 65)
3. Sex
4. Race (American Indian / Alaska Native, Asian, Black / African American, Native Hawaiian / Other Pacific Islander, White, Unknown)
5. Ethnicity (Hispanic, non-Hispanic)
6. Height
7. Weight

Baseline variables for participants will be:

8. D-dimer
9. SpO₂ and SpO₂/FiO₂
10. COVID ordinal scale score
11. Hematology labs: C-reactive protein, LDH, ferritin, leukocyte count, and platelet count in the blood
12. Temperature
13. Glomerular filtration rate (GFR)

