10.3 Secondary Efficacy Analyses

We will conduct secondary analyses on each component of the hierarchical composite endpoint:

- Time to death
 - *Analysis:* Cox proportional hazards regression
- Number of days on mechanical ventilation during study hospitalization
 - *Analysis:* Negative binomial regression
- Dichotomized (yes/no) decrease in SpO₂/FiO₂ ratio of at least 50 units relative to baseline at any time during the observation period
 - *Analysis:* Logistic regression

- Cumulative sum of COVID ordinal scores during study hospitalization
 - *Analysis:* Mann-Whitney U-test (nonparametric)

We will analyze an additional secondary endpoint:

- Days alive and free of organ support, where organ support is defined as receipt of invasive mechanical ventilation, vasopressor therapy, ECMO support, or incident dialysis
 - *Analysis:* Mann-Whitney U-Test (nonparametric)

Each analysis will include interactions of the study drug by stratification factor.

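### Baseline respiratory severity is recorded but enters no secondary clinical analysis by name, which costs some power and leaves estimates open to chance imbalance

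*SAP*

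**What the plan says.** SAP 8.3 sets the covariates for treatment comparisons: "Models to compare dipyridamole versus placebo will include both stratification factors as predictors: sex and age". It continues: "Where appropriate, models will include baseline values of the response variable". It does not list the endpoints to which this second sentence applies.

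SAP 10.3 names five secondary analyses:
- time to death, by "Cox proportional hazards regression"
- ventilator days, by negative binomial regression
- a drop in SpO2/FiO2 of at least 50, by logistic regression
- cumulative ordinal score, by Mann-Whitney test
- days alive and free of organ support, by Mann-Whitney test.

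It then says: "Each analysis will include interactions of the study drug by stratification factor". No severity term is named for any of them.

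SAP 9.4 lists "COVID ordinal scale score" among the baseline variables, which SAP section 9 tabulates descriptively. Randomisation is stratified by sex and age only (SAP 6.1, Protocol 8.1). Only invasive ventilation is excluded at entry (SAP 6.2.2). Hospitalised patients can therefore start anywhere from score 3 to score 5, the latter being "Non-invasive ventilation or high-flow oxygen" (SAP 6.4.10).

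**The concern.** A patient on high-flow oxygen at entry is plausibly nearer to ventilation and death than one on nasal prongs. The plan itself treats severity as relevant: the D-dimer power model in SAP 7.1 includes ICU status as a severity proxy. That idea does not reach the clinical outcomes, and the design does not balance severity between arms.

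If severity is prognostic, two things are at stake. An analysis that leaves it out is less powerful than one that uses a value already in the database. Also, whatever severity imbalance happens to arise moves the treatment estimate. Enrolment stopped at 100 (Protocol synopsis), so precision lost here cannot be regained by recruiting. If an imbalance is noticed only after the analysis, adjusting for it will look post hoc.

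**Working it through.** **1. What the baseline-value sentence supplies, endpoint by endpoint**

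| Secondary analysis | Usable baseline value of the response | Severity term as planned |
|---|---|---|
| Time to death (Cox) | None: all alive at entry | None |
| Ventilator days (negative binomial) | None: all not invasively ventilated | None |
| SpO2/FiO2 drop (logistic) | Possibly baseline SpO2/FiO2 | Not settled |
| Cumulative ordinal score (Mann-Whitney) | Baseline ordinal score | The test takes no covariates |
| Organ-support-free days (Mann-Whitney) | None usable | The test takes no covariates |

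The two Mann-Whitney tests cannot carry sex, age or the promised interactions either.

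**2. The plan's own figure**

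The documents give no power for any secondary endpoint. The nearest figure is the composite's 127 (SAP 7.2: win proportion 0.67, two-sided alpha 0.022, 80% power, 10% dropout). Noether's formula reproduces it:

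N = (2.290 + 0.842)² / (12 × 0.25 × 0.17²) = 9.809 / 0.0867 = 113.1, so 57 per arm, 114 in total. Then 114 / 0.9 = 126.7, so 127.

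**3. Power for a rank-type secondary endpoint (illustrative)**

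Assumptions: the same win proportion of 0.67, N = 100, and alpha 0.01. That alpha is the Bonferroni share for five analyses (SAP 8.7) if the family level is 0.05. Adjusting for a baseline score with correlation ρ to the outcome multiplies the variance by about (1 − ρ²):

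power = Φ( √(300 / (1 − ρ²)) × 0.17 − 2.576 )

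| ρ | 0 | 0.2 | 0.3 | 0.4 | 0.5 |
|---|---|---|---|---|---|
| Power | 0.64 | 0.67 | 0.70 | 0.74 | 0.80 |
| Equivalent N, 100/(1 − ρ²) | 100 | 104 | 110 | 119 | 133 |

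The documents give no value of ρ.

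**4. Power for a binary endpoint (simulation)**

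Assumptions, none from the documents: 50 per arm, 25–35% at score 5, event risk 15–20% at lower scores against 50–60% at score 5, odds ratio 0.35. Sex and age are in both models and the interactions are left out. Three settings within these ranges:
- Alpha 0.05, without and with severity: 0.37 and 0.41; 0.41 and 0.48; 0.48 and 0.51.
- Alpha 0.01, first set of runs: 0.13 and 0.15; 0.16 and 0.21; 0.23 and 0.24.
- Alpha 0.01, second set of runs: 0.13 and 0.15; 0.16 and 0.19; 0.24 and 0.27.

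The gain at 0.01 is thus about 1 to 5 points. With a stronger severity effect it is larger. With scores 3/4/5 split 20/60/20, a 35% control rate and odds ratio 0.33, an odds ratio of 5 per score category takes power from 0.25 to 0.32.

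For a rare outcome (5–10% against 20–30% by severity, 6 to 11 events), the gain at 0.01 is 0.2 to 1.2 points: 0.000 to 0.002, 0.012 to 0.015, and 0.030 to 0.042.

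**5. Type I error**

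Under no drug effect and without the score, simulated error was 0.042–0.051 at nominal 0.05 and 0.006–0.011 at nominal 0.01.

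**6. Chance imbalance**

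Assume 28% at score 5 and two independent binomial(50) draws. The SD of the difference between arms is √(2 × 0.28 × 0.72 / 50) = 0.090, or 9 points. By exact summation, a difference of 5 or more patients (10 points) has probability about 32%, and 8 or more (16 points) about 9%. The latter is 8–12% over the 25–35% range.

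Given 20% against 36% severe and no drug effect, the unadjusted odds ratio centres on about 1.4 and is significant at 0.05 in roughly 8–9% of trials. The adjusted one centres on 1.0, with about 4–6% significant.

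On a continuous scale, the between-arm difference in a baseline score has SD √(2/50) = 0.20 covariate SDs. An imbalance of 1.96 SDs shifts the unadjusted estimate by 1.96 × 0.20 × ρ, which is 0.12 (ρ = 0.3) to 0.20 (ρ = 0.5) outcome SDs. That is 19% to 32% of the effect implied by a win proportion of 0.67 (d ≈ 0.62).

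**The case against.** The strongest reply is that the plan is valid as written. Adjusting for the randomisation strata is a recognised choice, error rates are nominal, and adding a prognostic covariate is an efficiency preference. This stands as to validity. A reader might infer that unadjusted models are biased or produce too many false positives. Step 5 shows that they do not: the excess in step 6 holds only given a selected imbalance.

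A reader might also infer that a sizeable imbalance is to be expected. A 16-point gap arises in about one trial in eleven under the assumptions used, and a 10-point gap in about one in three. It is plausible, not likely.

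Nor is it correct that all five analyses adjust for sex and age alone. The baseline-value sentence could bring SpO2/FiO2, itself a severity measure, into the logistic model, and the rank tests adjust for nothing at all.

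The simulations are logistic, whereas the clearest gaps are in a Cox and a count model. The documents give no expected number of deaths. A Cox model that already holds treatment, sex, age and two interactions may not support another term. This stands, and it limits the remedy for death.

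Finally, the composite's interim analysis has been done and recruitment halted, so a covariate added now follows a look at related outcomes. This does not defeat the point. The score is a baseline measurement, and under SAP 8.1 the final analysis starts only after SAP approval, so the choice can still be fixed and dated in advance.

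**Conclusion.** The point holds for the time-to-death and ventilator-day models, where no baseline severity measure can enter as the SAP is written, and for the two Mann-Whitney tests. For the logistic model the SAP is unclear. The plan is not invalid and no primary result depends on this.

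The cost is a modest loss of power, about 1 to 5 points at alpha 0.01 under the assumed event rates. It would be greater if severity is strongly prognostic (about 15 points at ρ = 0.5 in the rank approximation) and close to nothing for rare deaths. Estimates are also sensitive to whatever severity imbalance occurred.

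All these sizes rest on assumed severity mixes, event rates and correlations, since the documents give none. The imbalance probabilities ignore any balance in severity that stratifying by age and sex may bring.

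**What to change.** Amend SAP 8.3 and 10.3 before the final analysis, stating for each endpoint which baseline value enters:
- **Ventilator days:** baseline ordinal score (5 versus 4 or less) as a main effect.
- **SpO2/FiO2 drop:** name either baseline SpO2/FiO2 or the baseline ordinal score as a covariate.
- **Cumulative ordinal score and organ-support-free days:** replace the plain Mann-Whitney test by a van Elteren test stratified by baseline ordinal score, and drop the promise of interactions for these two.
- **Time to death:** add the score only if the number of deaths supports it, for example in place of the treatment-by-stratum interactions or with a penalised fit. Otherwise report it as a sensitivity analysis. State the rule in terms of total deaths, not deaths by arm.

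Record the date of the change and that it was made without reference to results by arm.

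No new data are needed. The costs are one more parameter per model and, in the non-linear models, a treatment effect that is conditional on severity rather than marginal, which the report should say.

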8.4 Missing Data

We anticipate three sources of missing response data in this study: missing data entries, loss to follow-up, and early hospital discharge. We will summarize missingness for primary study endpoints. In preliminary results, a large majority of patients have early hospital discharge.

For the primary response and other longitudinal analyses, we address missing response data through random coefficients regression, which incorporates missingness through the standard errors of subject-level trend estimates. This strategy assumes missing entries are missing at random and that missing entries from early termination or discharge would not differ from the trend in the observed data. For time-to-event responses, we address early termination and discharge by right-censoring.

The DICER team will review data to minimize missingness in sex, age, and baseline values. Following Schafer et al. (1997), if these variables are missing for more than 5% of patients, we will impute them using SAS PROC MI and PROC MIANALYZE if necessary. Otherwise, we will exclude missing records from the analyses.

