10.16 Early Withdrawal Interaction

1. Record vital signs, oxygen requirements, and physical examination findings.
2. Review medical records to record data for endpoints
3. Concomitant medications review.
4. Review and record any Adverse Events.
5. Collect blood for clinical laboratory tests as described in the informed consent document.
 - a. 1x citrate tubes
 - b. 1x SST tube
 - c. 1x EDTA tube
6. Collect blood for research laboratory tests as described in the informed consent document.
 - a. 1x citrate tubes
 - b. 1x SST tube
7. Follow up call to participant for adverse events, 30 days after last dose of study drug

10.17 30 Days after last dose of study drug (\pm 2 day)

Chart review and follow up call to participant for AEs assessment up to 30 days after last dose of study drug (maximum of 44 days from initiation of trial participation).

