Mixed effects regression makes use of all available information for each subject -- even a subject with a single D-dimer measurement can be included. This technique efficiently makes use of the partial or full data observed from each subject, implicitly weighting subjects more if they have more observed points. We note that subjects who do well and are discharged relatively earlier will be somewhat down-weighted due to having fewer measurements, but this is appropriate since our primary aim is to assess moderation of D-dimer increase in-hospital. Discharge and other outcomes are discussed below as secondary aims. We also note that this approach quantifies the change in D-dimer as a linear trend on the log scale. Our preliminary analysis of D-dimer levels in patients with COVID-19 supports this simple approach to quantifying D-dimer variation. Although D-dimer can fluctuate from day-to-day, the longer-term trend is primarily linear, but we acknowledge that some patients may exhibit other patterns of change.

The second primary endpoint is a hierarchical composite of:

- Time of death from any cause during study duration
- Number of days on mechanical ventilation during study hospitalization
- Decrease in SpO₂/FiO₂ ratio of at least 50 units relative to baseline at any time during the observation period, and
- The cumulative sum of COVID ordinal scores during study hospitalization.

The composite endpoint will be nonparametrically assessed by comparing global composite rank score outcomes²⁴ across pairs of patients and evaluating a 'win ratio' using the Mann-Whitney U statistic. Each pair consisting of one treated and one untreated subject is ranked as defined below:

1. If both subjects die, then the subject who lives longer wins.
2. If exactly one subject dies, then the subject who does not die wins.
3. If the subjects are tied after step 2 (neither subject dies), then the subject with fewer days on ventilator wins.
4. If the subjects are tied after step 3, and only one of the subjects has a decrease in SpO₂ of 50 or greater, then the subject who does not have the decrease in SpO₂ wins.

5. If the subjects are tied after step 4, then the subject with lower Ordinal score wins.
6. If the subjects are tied after step 5, then their final result is a tie

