5.2 Endpoints

For convenience, we give names to the following times and time windows:

- Baseline or Day 1: Date of the first study drug administration
- Study Hospitalization: Day 1 through either Day 14 or hospital discharge, whichever is first
- Observation Period: The 28-day period following first study drug administration
- Study Duration: The period from baseline until 30 days after last study drug administration

If an endpoint is to be evaluated at all three of the above time points, we use the phrase ‘at any time point’.

Endpoints are presented in a numbered list to facilitate references to endpoints when conducting the final analysis.

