5.2.1 Primary Endpoint

The first co-primary endpoint is increase in plasma D-dimer levels compared to baseline.

The second co-primary endpoint is a clinical hierarchical composite of:

- Time to death from any cause during study duration
- Number of days on mechanical ventilation during study hospitalization
- A dichotomized (yes/no) decrease in daily average SpO₂/FiO₂ ratio of at least 50 units relative to Day 1 at any time during the observation period
- Cumulative sum of COVID ordinal scores during study hospitalization

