6.3 Study Assessments

Table 1. Schedule of Events

Study Day	Screening Enrollment	Day 1	Days 3, 7, 11	Days 5, 9, 13	Even Days 2-12	Day 14	Day 28	Early Withdrawal	30 Days After Drug
Screening via chart review	X								
Screening for eligibility	X								
Informed consent	X								
Pregnancy test ^a	X								
Demographics		X							
Medical history		X							
Social history ^b		X							
Physical exam SOC review ^c		X							
Randomization	X								
Study drug administration		X	X	X	X	X			
Vitals/Oximetry SOC review ^c		X	X	X	X	X	X ^j	X	
Respiratory status SOC review ^c		X	X	X	X	X		X	
Clinical progress review		X	X	X	X	X		X	
Clinical care lab result review		X	X	X	X	X		X	
ECG clinical care data review ^d		X	X	X	X	X		X	
Chest imaging review ^d		X	X	X	X	X		X	
BMP ^e		X	X	X				X	
D-dimer ^e		X	X	X		X		X	
Ferritin ^e		X		X				X	
LDH ^e		X		X				X	
CRP ^e		X		X				X	
CBC w/ diff ^e		X	X	X		X		X	
FBN ^e		X	X	X		X		X	
PTT/INR ^e		X	X	X		X		X	
ABG ^d		X							
LFT ^e		X		X				X	
Research blood draw ⁱ		X ^f	X ^f	X ^f				X	
Concomitant meds/therapies		X	X	X	X	X	X ^g	X	
AE assessment		X	X	X	X	X	X ^g	X	X ^h

a Performed in subjects of child-bearing potential, if not already performed for clinical care reasons

b Social history including pregnancy history, tobacco and alcohol use

c Medical chart review for extraction of standard-of-care data.

d Only if performed while patient is inpatient/hospitalized for clinical care reasons. Data will be recorded.

e Lab results will be extracted from blood drawn for clinical care, whenever possible..

f Blood collection will be coordinated with blood draw for clinical care lab studies, whenever possible.

g Medical chart review for secondary endpoints will continue until Day 28.

h Chart review and phone call for AEs assessment until 30 days after last dose of study drug, maximum of 44 days from initial participation date.

i: Research lab draws on study days 3,5,9,11,13 will have +/- 1 day window.

Prior to conducting any study-related activities, written informed consent containing Health Insurance Portability and Accountability Act (HIPAA) authorization will be signed and dated by the participant.

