
[1] Death and survival are assessed from the time of study medication to 30 days after the last dose of study drug (a maximum of 44 days from consent). Participants are censored at the time of drop-out or the data cutoff date (if no event has occurred).
 
[2] Number of days on mechanical ventilation are counted from the time of study medication until hospital discharge. If a participant is re-hospitalized and receives ventilation, these data are not counted.
 
[3] Oxygenation measurements are collected from EHR records. Baseline is defined as the average of measurements taken between 8 hours prior to start of study medication and the start of study medication administration. A 50-point drop is defined as a participant who experiences two consecutive measures of at least 50 points below baseline. Post-baseline measurements are assessed up to and including day 44 (from consent).
 
[4] COVID ordinal scores are defined in Table 2.
						

The cumulative sum of COVID ordinal scores used in Step 6 is calculated as the time-weighted sum of daily ordinal scores, with units of ordinal score days. For example, if a subject started medication at 9:00 pm on Day 1 with a score of 4, and that score decreased to 3 at 6:00 am the next day, and that patient was discharged at noon on the third day, then the cumulative sum of ordinal scores would be:

$$\frac{\{3 \text{ hrs} \times 4 + (6 \text{ hrs} \times 4 + 18 \text{ hrs} \times 3) + 12 \text{ hrs} \times 3\}}{24 \text{ hrs/day}} = \frac{12 + (24 + 54) + 36}{24} = 5.25$$

The use of the cumulative ordinal score in Step 6 of the above algorithm is meant as a combined measure of the severity and duration of a patient's illness, since longer hospitalizations and larger daily ordinal scores will both increase the cumulative total.

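### SAP 8.4 censors time-to-event responses at discharge with no exception for death, while other sections follow death past discharge and the secondary Cox model in SAP 10.3 names no rule

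*SAP*

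**What the plan says.** SAP 8.4 lists early discharge as a source of missing response data, reports that most patients so far were discharged early, and sets this rule: "For time-to-event responses, we address early termination and discharge by right-censoring". It does not limit the rule to particular endpoints.

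Death is treated differently elsewhere:

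- SAP 5.2.1 defines the component as "Time to death from any cause during study duration". SAP 5.2 defines that window: "Study Duration: The period from baseline until 30 days after last study drug administration". Dosing stops at discharge or Day 14 (SAP 6.1), so for patients discharged early most of the window lies after discharge.
- SAP 6.1: "Clinical data capture and survival follow-up occurred on Day 28" (± 1), with further follow-up 30 days after the last dose.
- SAP 6.3, Table 1 note g: "Medical chart review for secondary endpoints will continue until Day 28".
- SAP Table 3 note 1, written for the win ratio: "Participants are censored at the time of drop-out or the data cutoff date (if no event has occurred". Discharge is not a censoring event there.
- Protocol 3.2 collects days to mortality through 28 ± 1 days.
- Protocol 10.17: "Chart review and follow up call to participant for AEs assessment up to 30 days after last dose of study drug".

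SAP 10.3 and Protocol 15.4 say only that time to death is analysed by Cox regression. Neither gives a window or a censoring rule.

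**The concern.** An analyst programming the SAP 10.3 Cox model finds one explicit instruction for time-to-event data, and it says to censor at discharge. Another analyst, reading the endpoint definition or the win-ratio footnote, would follow vital status for weeks longer. Both could claim to follow the SAP, and they could report different mortality hazard ratios.

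The discharge rule also censors informatively. Patients go home because they are recovering; Protocol 15.3 makes the link when it notes that "subjects who do well and are discharged relatively earlier will be somewhat down-weighted due to having fewer measurements". Removing them at discharge leaves a risk set that grows sicker, and it does so sooner in the arm that discharges sooner. A drug that shortened stay without changing mortality would appear to raise the death hazard. A drug that did both could have its mortality benefit hidden.

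**Working it through.** **1. The follow-up window.** SAP Table 3 note 1 gives a maximum of 44 days, which reproduces: 14 treatment days + 30 = 44. For a patient whose last dose is on the day of discharge, observation for death ends on:

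| Discharge day | SAP 8.4 as written | Protocol 3.2 | SAP 5.2 / Table 3 | Share of SAP 5.2 window kept by 8.4 |
|---|---|---|---|---|
| 3 | 3 | 28 | 33 | 3/33 = 9% |
| 5 | 5 | 28 | 35 | 5/35 = 14% |
| 7 | 7 | 28 | 37 | 7/37 = 19% |
| 10 | 10 | 28 | 40 | 10/40 = 25% |
| 14 | 14 | 28 | 44 | 14/44 = 32% |

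**2. SAP 8.4 cannot be universal.** Time to hospital discharge (SAP 5.2.4, item 9) is also a time-to-event response. If discharge censored it, it would have no events. The rule needs limiting by endpoint, and the SAP does not do so.

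**3. Why the censoring is informative.** Take an arm of 50 with 35 discharged alive, followed by 5 deaths among the 15 still in hospital. With full follow-up, mortality is 5/50 = 10%. With censoring at discharge, Kaplan-Meier gives 1 − (14/15)(13/14)(12/13)(11/12)(10/11) = 1 − 10/15 = 33%.

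**4. Effect on the hazard ratio.** The documents give no mortality rate or stay, so these inputs are assumed: mortality p = 12% in both arms; death at 1 + Gamma(shape 2, scale 6) days; all deaths in hospital; survivors' discharge exponential with median m, so G(t) = 2^(−t/m); m = 7 on placebo; analysis to Day 28.

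The share still at risk at time t is p·S(t) + (1 − p)·G(t), where S is survival among those who will die. Deaths occur at the same rate in both arms, so the apparent hazard ratio at t is the placebo risk set divided by the drug risk set. For m = 7 against 5:

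- Day 7, S = 0.736: (0.12×0.736 + 0.88×0.500)/(0.12×0.736 + 0.88×0.379) = 0.528/0.422 = 1.25
- Day 14, S = 0.363: (0.12×0.363 + 0.88×0.250)/(0.12×0.363 + 0.88×0.144) = 0.264/0.170 = 1.55
- Day 21, S = 0.155: (0.12×0.155 + 0.88×0.125)/(0.12×0.155 + 0.88×0.0544) = 0.1286/0.0664 = 1.94

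The Cox model averages these. Simulated Cox hazard ratios (2,000,000 per arm), with the true value 1.00:

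| Drug-arm median stay | Censored at discharge | Followed to Day 28 | Followed to last dose + 30 days |
|---|---|---|---|
| 7 | 1.00 | 1.00 | 1.00 |
| 6 | about 1.17 | 1.01 | 1.01 |
| 5 | 1.44 | 1.00 | 1.01 |
| 4 | 1.90 | 1.00 | 1.02 |
| 9 | 0.80 | 1.00 | 1.00 |

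At 7 against 5 days, the share censored at discharge before Day 28 is 0.88×(1 − 2^(−28/7)) = 83% on placebo and 0.88×(1 − 2^(−28/5)) = 86% on drug. Mean follow-up for death falls from 26 days to 9.8 and 7.7.

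**5. Sensitivity.**

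- Over 45 scenarios (mortality 5, 12 or 20%; three death-time scales; five discharge distributions), discharge censoring gives 1.09–1.43 (6 days), 1.27–2.06 (5), 1.47–3.58 (4) and 0.56–0.88 (9). Day 28 follow-up gives 0.96–1.04.
- Discharge unrelated to prognosis: 1.00–1.01, so no bias.
- True mortality 12% against 8%: with equal stay, 0.68 instead of 0.66. With 7 against 5 days, 1.01 instead of 0.66.
- 20% of deaths after discharge: about 19% of deaths to Day 28 are lost, and the hazard ratio at 7 against 5 days is 1.46.

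**6. Test error.** In 4,000 null trials of 50 per arm, rejection at 0.05 and at the Bonferroni level 0.05/5 = 0.01 was:

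| Stay, placebo vs drug | Score test | Wald test |
|---|---|---|
| 7 vs 5 days | 9.8%, 2.7% | 6.7%, 1.0% |
| 7 vs 4 days | 19.7%, 7.5% | 15.7%, 3.8% |
| Any stay, either longer follow-up window | about 5%, 1% | about 3%, 0.1% or less |

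**The case against.** The strongest reply is that SAP 8.4 deals with missing data. It tells the analyst what to do when discharge leaves a response unobserved, as with time to oxygenation improvement, which depends on hospital oximetry. Death is still observed after discharge. SAP 5.2.2 and 10.3 make the secondary endpoint a component of the composite, and that component is defined over study duration; a specific definition normally overrides a general sentence. Protocol 3.4 already gives time to discharge its own rule, with death as a competing risk and loss to follow-up as the censoring event, so endpoint-specific rules were evidently in mind.

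This makes following death past discharge the likely intent. But SAP 8.4 names discharge itself as the reason for censoring, SAP 5.2.2 sets no censoring rule for the Cox model, and SAP 10.3 does not cite Table 3 note 1.

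The second reply is about size. The bias needs three things together: the literal reading, a difference in stay, and discharge tied to prognosis. A stay shortened by 2 or 3 of 7 days is large for a trial that stopped recruiting for futility. At 50 per arm and 12% mortality the standard error of the log hazard ratio is about 0.63, so the 95% interval spans a factor of exp(1.96×0.63) ≈ 3.4 either way. At 7 against 5 days the Wald test stays near its nominal Bonferroni level. The simulations also omit the stratum interactions that SAP 10.3 requires. These points are fair. They keep the matter to the reported estimate of one secondary endpoint, but they do not remove the conflict.

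**Conclusion.** The concern holds. The conflict rests on the documents alone: the SAP's only general censoring rule for time-to-event data contradicts how death is defined and followed elsewhere, and the Cox model for death is left without a rule of its own.

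How much it would matter is conditional. Under the assumed base case, applying SAP 8.4 to death moves a true hazard ratio of 1.00 to about 1.17, 1.44 or 1.90 when the drug arm's median stay is 6, 5 or 4 days against 7, and to 0.80 when it is 9. It can also turn a real 0.66 into 1.01. With equal stays the effect is nil or small, and if discharge is unrelated to prognosis there is none.

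The damage is confined to one secondary endpoint, though that endpoint is mortality and is one of five tests under the Bonferroni adjustment in SAP 8.7. The co-primary win ratio, the alpha allocation and the sample size of 127 are unaffected. This should be corrected; it does not threaten the trial's main conclusions.

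**What to change.** Add to SAP 8.4: *Discharge does not censor time to death. Vital status after discharge is used. Participants are censored only at withdrawal or loss to follow-up, at data cutoff, or at the end of the death follow-up window.* State the same rule in SAP 10.3, for example by citing Table 3 note 1.

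Separately, reconcile the death window between Protocol 3.2 (28 ± 1 days) and SAP 5.2.1 with Table 3 note 1 (30 days after last dose), and use one. A fixed Day 28 horizon is an option. The longer window gave 1.00–1.02 in the base case and is not shown to be materially biased.

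The cost is two sentences and the definition of one censoring variable. Survival follow-up at Day 28 and the chart review and call to 30 days after last dose are already planned, so no new data are needed.
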